## Protocol

### Study design and participants

This is a single-center prospective quasi-randomized controlled trial, recruiting children aged 2 to 18 years who require hospitalization for CAP in the Department of Pediatrics, The Lady Davis Carmel Medical Center in Haifa, Israel. The study has been approved by the Carmel Medical Center institutional review board (approval number CMC-0170-16), and a parent has to give a written informed consent before recruitment. Exclusion criteria comprised of children who are hemodynamically unstable or required transfer to an intensive care unit; children with other systemic comorbidities or chronic respiratory diseases, including but not limited to congenital bronchopulmonary malformations, Cystic Fibrosis, immune compromise, genetic malformations, and congenital heart disease (excluding patent foramen ovale and atrial septal defect); children from families unable to comprehend and sign an informed consent form.

To determine the sample size required to establish a difference in the hospitalization duration in the study population, given confidence level of 95% and power of 80%, to detect a difference of 0.8 standard deviation (SD) in hospitalization duration between the intervention group and the control group, a sample size of 26 subjects in each group is needed.

Following a senior doctor's diagnosis of CAP based on the combination of clinical, laboratory and radiological results in the Emergency Department, the criteria for admission included at least one of the following: hypoxemia, dehydration, inability to take oral medications, moderate-to-severe respiratory distress, toxic appearance, complicated pneumonia (such as medium-to-large pleural effusion, empyema, lung abscess, pneumatocele, or necrotizing pneumonia), or failure of oral antibiotic treatment (2,28). All these patients were presumed to have bacterial pneumonia and

were treated with antibiotics though we did not specifically test for viral or bacterial origin.

The hospitalized children are randomly assigned to either the intervention or control group based on their order of arrival in a 1:1 case-control and were treated in separate rooms. Both groups receive comparable medical treatment (as needed intravenous (IV) antibiotics, adequate respiratory support, hydration, pain and antipyretic treatment) and investigations, with the intervention group additionally receiving 15-minute visits from MCs twice daily during the first two days of admission.

The medical clowns in this study are part of 'The Dream Doctors Project', a unique Israeli non-profit organization that integrates professional medical clowns into Israeli hospitals, training them to work as members of multidisciplinary care teams. These clowns used various techniques to relax the patients (e.g. music, singing, playing, humor, guided imagination) and helped encourage children to begin drinking and eating on their own.

All laboratory and radiology tests, as well as treatment decisions, including admission and discharge, are based solely on clinical judgment by pediatricians who were blinded to the study and not involved in it (the clinical team was separate from the research team). Criteria for discharge are based on the IDSA Clinical Practice Guidelines for CAP. In our department, discharges occur at the same rate on weekends as on weekdays, so the length of hospitalization should not be affected by weekend admissions.

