### Study assessments

A doctor's daily case report form (CRF) (Supplementary 1) and a parent CRF (Supplementary 2) must be completed on the first two days of admission. In both groups, the child's primary caregiver, who accompanies them during the hospital stay

should answer the parent CRF. These forms document details of child's treatment, clinical assessment, vital signs, symptoms, and overall well-being as perceived by a parent (regarding respiratory state, mood and vitality) and the treating doctor (regarding pain, mood and vitality). The well-being variables will be evaluated by a visual analogue scale (VAS) in the CRF's grading their opinion between 1 (lowest score) to 10 (best score) except for pain where VAS meaning was 1= not suffering at all to 10 = most suffering.

The primary outcome parameter is length of hospitalization in hours, determined by the duration between admission and discharge from the pediatric department. Secondary outcome parameters include the duration of IV treatment, need for chest tube insertion, changes in well-being scores as reported by both the parent and the treating physician, and alterations in vital signs and laboratory results.

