#### Statistical analysis

Statistical analyses will be performed using IBM statistics (SPSS) vs 24. The continuous variables will be presented by mean and SD or Median and IQR, as appropriate. The categorical variables will be presented in percentages. To check differences between the two groups, Chi square test will be used for the categorical variables and independent t-test, or Mann Whitney for the continuous variables.  $P < 0.05$  is considered statistically significant.

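### Children are called randomly assigned but are allocated by order of arrival, with no exact rule and no concealment; under alternation the next arm is predictable

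*Combined protocol and SAP*

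**What the plan says.** Under Study design and participants, the protocol opens: "This is a single-center prospective quasi-randomized controlled trial". Later in the same section the allocation is described as follows: "The hospitalized children are randomly assigned to either the intervention or control group based on their order of arrival in a 1:1 case-control". On consent, it says that "a parent has to give a written informed consent before recruitment". It does not say that the next arm is hidden at that moment.

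The same section covers who makes clinical decisions. Tests and treatment decisions, "including admission and discharge, are based solely on clinical judgment by pediatricians who were blinded to the study and not involved in it", with the note that "the clinical team was separate from the research team". It does not say who approaches families or who applies the allocation.

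Admission requires "at least one of the following: hypoxemia, dehydration, inability to take oral medications, moderate-to-severe respiratory distress, toxic appearance, complicated pneumonia" or failure of oral antibiotics. The complicated forms listed include empyema and necrotizing pneumonia.

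Under Study assessments: "The primary outcome parameter is length of hospitalization in hours, determined by the duration between admission and discharge from the pediatric department". Under Statistical analysis, the group comparison is an "independent t-test, or Mann Whitney for the continuous variables". No adjustment for baseline severity is planned.

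**The concern.** One allocation step carries three descriptions that do not fit together: random, quasi-randomized, and case-control. The operative rule, order of arrival, is deterministic, so the word *randomly* claims a protection that the design does not have.

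The text leaves four things open:

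- the exact rule (alternation, odd and even numbers, or something else);
- whether order is counted among all arrivals or only among consented children;
- who approaches families;
- whether the next assignment is concealed until the child is enrolled.

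If the rule is alternation, anyone who knows the last assignment knows the next. A recruiter could then, knowingly or not, approach or persuade families differently according to the arm due. Expected stay can vary widely across the admission criteria. With 26 children per arm and an unadjusted test, any severity imbalance that arises this way passes straight into the primary comparison.

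**Working it through.** **The plan's own figure.** Inputs from Study design and participants: difference 0.8 SD, 95% confidence, 80% power. The normal approximation gives n = 2(1.960 + 0.842)² / 0.8² = 24.5, so 25 per group. The t-test calculation gives 25.52, so 26 per group, with power 80.7% at 26. The stated 26 reproduces and is not in dispute.

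**Predictability over 52 children.** Under strict alternation (assumed) the first child is a 50% guess and the other 51 are certain: (0.5 + 51)/52 = 99.0% correct guesses expected. Simple randomization gives 50%.

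**What a modest use of that knowledge could do.** None of the following inputs is in the documents; all are assumptions. Severity is standard normal and correlates r = 0.3, 0.5 or 0.7 with stay. There is no true effect. A recruiter knows the arm due, recognises the most severe fifth, and does not enrol some or all of them when the intervention is due.

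- Children passed over to fill 26 intervention places: half of the fifth, 26 × 0.1/0.9 = 2.9; all of it, 26 × 0.2/0.8 = 6.5.
- Shift in mean severity in the intervention arm: the cut-off for the top fifth is 0.842, where the normal density is 0.280. Removing half gives −0.5 × 0.280/0.9 = −0.156. Removing all gives −0.280/0.8 = −0.350.
- Bias in stay, in SD: −0.156r = −0.047, −0.078, −0.109 and −0.350r = −0.105, −0.175, −0.245.

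Simulation (40,000 trials per scenario, 26 per arm, two-sided 5%, Monte Carlo error about 0.1 to 0.2 percentage points) agrees on the bias and gives these false-positive rates. The last column assumes a log SD of 0.5.

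| Severe fifth passed over | r | Bias (SD) | t-test | Mann-Whitney | t-test, log-normal stay |
|---|---|---|---|---|---|
| Half | 0.3 | −0.047 | 5.3% | 5.1% | 5.0% |
| Half | 0.5 | −0.077 | 5.8% | 5.5% | 5.7% |
| Half | 0.7 | −0.107 | 6.7% | 6.3% | 6.8% |
| All | 0.3 | −0.105 | 6.6% | 6.2% | 6.3% |
| All | 0.5 | −0.175 | 9.6% | 8.9% | 10.0% |
| All | 0.7 | −0.246 | 14.5% | 13.4% | 16.7% |

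With nobody passed over, all three tests reject in 4.7% to 5.0% of trials. Against the planned 0.8 SD, the bias is 0.047/0.8 = 6% to 0.107/0.8 = 13% (half) and 0.105/0.8 = 13% to 0.246/0.8 = 31% (all).

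**How far later adjustment helps.** Adjusting for an exact indicator of the severe fifth restores 4.9% to 5.1%. Two imperfect yes/no markers (assumed latent correlation 0.7 with severity, prevalence 40% and 20%) leave about half the bias: 0.023 to 0.053 SD with half passed over and 0.055 to 0.131 SD with all. False positives are then 5.0% to 5.3% and 5.4% to 8.0%.

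**If the method changed midway.** With 13 per arm by order of arrival (all severe passed over) and 13 per arm by concealed list, over 30,000 trials, the bias is 0.052, 0.087 and 0.123 SD for the three values of r. Adjusting for phase alone leaves it unchanged (false positives 5.4% to 7.2%). Phase plus the exact severity indicator gives 4.9% to 5.1%.

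**The case against.** The strongest reply is that the method is disclosed: quasi-randomized is the usual term for allocation by a non-chance rule, and beside it the other words are loose drafting. That is partly right. But the label gives neither the rule nor any concealment, and the allocation sentence contradicts it.

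Second, the harm needs a chain of conditions that the documents do not establish: alternation, a recruiter who tracks it, recognition of severe cases, and selective enrolment. The direction is assumed too. A recruiter who wanted clowns for the sickest children would bias the result the other way. All of this stands, which is why the figures are illustrative. The milder scenario is indeed close to nominal error.

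Third, the plan has safeguards. Unstable and intensive-care children are excluded, which trims the severe end. The clinicians who decide admission and discharge are described as blinded, which limits steering through those decisions. Yet complicated pneumonia stays eligible, and neither safeguard governs whom the research team approaches or who consents.

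Fourth, the mixed tenses may mean that enrolment is complete, so a new sequence could not be applied. Then the weakness cannot be removed, but it can still be described correctly and partly examined.

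**Conclusion.** The concern holds and should be fixed. The allocation is not random as described, the rule is incomplete, and nothing in the text hides the next arm from those who recruit. This conclusion rests on the wording alone and does not depend on the simulated sizes.

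The possible effect on the primary result runs from slight (bias about 0.05 SD, false-positive rate near 5%) to material (about 0.25 SD, 15% with the t-test and up to 17% with log-normal stay). It depends on the assumed correlation and on how much selection occurs. These figures also assume alternation and a recruiter who acts on it. Nothing in the documents shows that steering took place.

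**What to change.** **If enrolment is open**, replace the allocation sentence with:

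> After eligibility is recorded and consent is signed, children are allocated 1:1 by a computer-generated list in permuted blocks of varying size, prepared by a person not involved in recruitment and concealed in sequentially numbered opaque sealed envelopes, each opened only at that point.

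Delete the references to order of arrival and case-control. Remove the prefix *quasi-* only if no child has yet been allocated by order of arrival. Otherwise keep it, describe both allocation phases, show results by phase, and include phase together with the severity covariates in the adjusted analysis. Keep block sizes undisclosed: with blocks of 4, 6 and 8 (assumed), someone who knows all past assignments would still guess about 68% correctly, against 99.0% under alternation.

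**For children already allocated by order of arrival:**

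1. Delete *randomly* and *case-control*.
2. State the rule used and whether order was counted before or after consent.
3. Report children approached, refused and excluded by the arm due, where records exist.
4. Add to Statistical analysis:

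> As a sensitivity analysis, log length of stay will be regressed on arm and on severity features recorded in the Emergency Department before allocation (for example hypoxemia and complicated pneumonia).

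Keep the covariates few, because there are only 52 children; others may be chosen from the admission list. Fix them before outcomes are seen by arm, or label the analysis post hoc. State that adjustment reduces bias from measured severity only.

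**Cost.** With enrolment open: an amendment, a generated list and envelopes. With enrolment closed: corrected wording, counts from existing records and one regression on data already used at admission. The sample size stays at 26 per arm in both cases.

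### Change in laboratory results is compared between arms only among children whose clinicians chose to retest them, which exposes this secondary outcome to selection bias.

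*Combined protocol and SAP*

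**What the plan says.** All references are to the combined protocol and SAP.

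- **Who orders tests.** Study design and participants: "All laboratory and radiology tests, as well as treatment decisions, including admission and discharge, are based solely on clinical judgment". The decisions are made "by pediatricians who were blinded to the study and not involved in it".
- **The outcome.** Study assessments lists "alterations in vital signs and laboratory results" among the secondary outcomes. It names no analyte, time point or repeat sample.
- **What must be collected.** The doctor and parent forms are required on the first two days. "These forms document details of child's treatment, clinical assessment, vital signs, symptoms, and overall well-being". Vital signs are in that list; laboratory tests are not.
- **First value.** Diagnosis is "based on the combination of clinical, laboratory and radiological results in the Emergency Department", so most children probably have an initial result.
- **Observation window.** The primary outcome is "length of hospitalization in hours, determined by the duration between admission and discharge from the pediatric department", so the time in which a repeat test can occur ends at the event that defines the primary outcome.
- **Analysis.** Under Statistical analysis, "To check differences between the two groups" the plan uses a t-test or Mann-Whitney test for continuous variables at P < 0.05. It gives no rule for children without a second value and does not ask for the number retested per arm.

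**The concern.** A change needs two values, and the second exists only if a clinician asks for it before the child goes home. Ordering a repeat and discharging the child both plausibly depend on how the child is doing, which is what the intervention is meant to improve. The children who enter the laboratory comparison are then selected after allocation, by a process the intervention may affect. Balanced allocation protects a comparison of the full arms; it does not protect one made in such a subset.

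If the intervention works, fewer intervention children may be retested, and those who are would tend to be the slower recoverers of that arm. A real laboratory gain could be shrunk or missed, and a null result could be published as evidence about the intervention when it partly reflects who was retested. The sample is also smaller than 26 per group.

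**Working it through.** **1. The plan's own figure.** Inputs from Study design and participants: difference 0.8 SD, 95% confidence, 80% power. A two-sided t-test needs 25.5 per group, rounded up to 26, with power 80.7%. The stated 26 reproduces. It refers to length of stay, which is observed in every child.

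**2. Loss of numbers alone.** Retest shares are assumed, equal in both arms, with no selection:

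| Share retested | n per arm | Power at 0.8 SD | Detectable at 80% power |
|---|---|---|---|
| 100% | 26 | 80.7% | 0.79 SD |
| 80% | 21 | 72% | 0.89 SD |
| 60% | 16 | 59% | 1.02 SD |
| 40% | 10 | 40% | 1.32 SD |

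**3. Selection model.** Recovery R has SD 1, with mean 0 in controls and *d* in the intervention arm. Laboratory improvement L has SD 1 and correlation ρ with recovery within arm. Only *d* = 0.8 has a counterpart in the documents (the design difference for length of stay). *d* = 0.4, ρ = 0.3 to 0.7, the retest shares and the retest rules are assumptions.

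*Sharp threshold: a child is retested if R < c.* The control share is Φ(c) and the intervention share Φ(c − d). The bias in mean L (intervention minus control) is

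ρ × [φ(c)/Φ(c) − φ(c − d)/Φ(c − d)].

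- Largest: 50% of controls retested (c = 0), d = 0.8. Intervention share Φ(−0.8) = 21%. Bracket: 0.798 − 1.367 ≈ −0.57. With ρ = 0.7 the bias is −0.40 SD.
- Smallest: 70% of controls (c = 0.524), d = 0.4. Intervention share Φ(0.124) = 55%. Bracket: 0.497 − 0.720 ≈ −0.22. With ρ = 0.3 the bias is −0.07 SD.
- Children analysed: 26 × 0.21 to 26 × 0.55, about 5 to 14, against 26 × 0.50 to 26 × 0.70, about 13 to 18.

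*Probabilistic retesting: logit P(retest) = a − s × R*, with s = 1 or 2 and *a* set so that 40%, 60% or 80% of controls are retested.

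- Largest (40% of controls, s = 2, d = 0.8, ρ = 0.7): intervention share 20%, bias −0.23 SD.
- Smallest (80% of controls, s = 1, d = 0.4, ρ = 0.3): intervention share 74%, bias about −0.015 SD, quoted below as about 0.02.

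**4. If laboratory gain follows recovery.** Let the true laboratory benefit be ρ × d. With ρ = 0.5 and d = 0.8 it is 0.40 SD.

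- Probabilistic, 60% of controls retested, s = 2: 60% v 36% retested. Observed 0.40 − 0.15 = 0.25 SD.
- Threshold, 50% of controls retested: 50% v 21% retested. Observed 0.40 − 0.285 ≈ 0.12 SD.

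The observed difference stays positive in every setting examined, so the effect is attenuation.

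**5. When there is no bias.** It is zero if d = 0, if ρ = 0 or if s = 0. With d = 0, simulated trials of 26 per arm under the threshold rule reject in about 5%, as intended.

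**The case against.** The strongest reply is that nothing in the documents says how often, when or why children are retested. That fast recoverers are retested less is an inference. The forms themselves (Supplementary 1 and 2) are not in the supplied text, and routine retesting in the department cannot be excluded. This stands: the size cannot be taken from the documents, and the point is one of exposure to bias.

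A second reply cites the safeguards: blinded ordering, and the statement that "Both groups receive comparable medical treatment" and investigations. These address ordering that differs because the arm is known. They do not address ordering that responds to the child's course, which needs no knowledge of the arm, and no test schedule stands behind the word comparable.

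A reader might go further and infer that the laboratory comparison is definitely biased, or that it will show a false laboratory disadvantage. The documents support neither. There is no bias under the conditions in step 5. A false disadvantage requires faster recovery with no laboratory gain at all, which sits poorly with a correlation of 0.3 to 0.7 between the two. Even then, under the harsher threshold rule with 26 per arm, a significant false disadvantage appears in about 4-16% of simulated trials (nominal 2.5%), and in most settings below 10%. The error also runs against the intervention, so on this model it is not a route to a false efficacy claim.

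Finally, dropping the p value does not remove the selection from the paired values. That is correct, and is why those values need a label and the retest counts beside them.

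**Conclusion.** The concern holds in a conditional form. The plan makes laboratory change an outcome tested between arms but leaves the second measurement to clinical judgment, so the comparison is confined to a subset formed after allocation. If retesting follows recovery and the intervention speeds recovery, the likely result is a laboratory benefit that is shrunk or hidden.

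The assumed ranges give about 0.02 to 0.23 SD against the intervention with probabilistic retesting and 0.07 to 0.40 SD with a sharp threshold. The second range uses the harshest form of selection and should not be quoted without the first. The planned test is sound only if one of the no-bias conditions holds, and the plan neither states nor checks them.

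The scope is one secondary outcome. Length of stay is not touched, and the point does not extend to vital signs, which the forms record on the first two days. It is a cheap improvement worth making.

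**What to change.** - In Study assessments and in Statistical analysis, state that laboratory change is descriptive, with no between-arm p value and no efficacy statement.
- Report admission laboratory values for all allocated children as baseline data.
- Report per arm, with all allocated children as the denominator, the number retested and the timing of the repeat tests.
- Show paired values by arm, labelled as coming from a subset selected by clinicians.

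This needs no extra sampling and no change to care. The cost is a few sentences and a significance claim on one secondary outcome.

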### Study assessments

A doctor's daily case report form (CRF) (Supplementary 1) and a parent CRF (Supplementary 2) must be completed on the first two days of admission. In both groups, the child's primary caregiver, who accompanies them during the hospital stay

should answer the parent CRF. These forms document details of child's treatment, clinical assessment, vital signs, symptoms, and overall well-being as perceived by a parent (regarding respiratory state, mood and vitality) and the treating doctor (regarding pain, mood and vitality). The well-being variables will be evaluated by a visual analogue scale (VAS) in the CRF's grading their opinion between 1 (lowest score) to 10 (best score) except for pain where VAS meaning was 1= not suffering at all to 10 = most suffering.

The primary outcome parameter is length of hospitalization in hours, determined by the duration between admission and discharge from the pediatric department. Secondary outcome parameters include the duration of IV treatment, need for chest tube insertion, changes in well-being scores as reported by both the parent and the treating physician, and alterations in vital signs and laboratory results.

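### The supplied text neither places the first CRF before the first clown visit nor defines change in well-being, and it plans only unadjusted tests; a secondary contrast could be diluted

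*Combined protocol and SAP*

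**What the plan says.** Study design and participants gives the intervention arm "15-minute visits from MCs twice daily during the first two days of admission". Study assessments asks for the doctor's daily CRF and says that "a parent CRF (Supplementary 2) must be completed on the first two days of admission". The forms record, among other things, "clinical assessment, vital signs, symptoms, and overall well-being as perceived by a parent", with visual analogue items scored by "grading their opinion between 1 (lowest score) to 10 (best score) except for pain", which runs the other way.

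The secondary outcomes include "changes in well-being scores as reported by both the parent and the treating physician, and alterations in vital signs and laboratory results". No time points are attached to these changes or alterations. For continuous variables, Statistical analysis names only the "independent t-test, or Mann Whitney for the continuous variables". It mentions no covariate and no repeated-measures model.

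**The concern.** Visits and forms share the same two days, and nothing in the supplied text fixes their order on day 1. The clowns use music, play and humor to relax the child, so a visit could plausibly lift mood at once. A control child's first form is always free of clown exposure. A clown-arm child's first form may or may not be. Any early effect captured on late first forms therefore sits in one arm only and does not cancel when day 1 is subtracted from day 2.

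At stake are the outcomes closest to what the clowns do: the parent and physician scores, and the vital signs on the same forms. A real benefit could look small or absent when expressed as change. Because the contrast is not defined, it could also be chosen after the data are seen.

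A second, milder point is that the first score is collected anyway, but the plan does not use it as a covariate, so available precision is given up.

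**Working it through.** **The plan's own figure.** For a 0.8 SD difference in length of stay, 80% power and 5% significance (two-sided assumed), the normal approximation gives 25 per group. The exact noncentral t calculation gives 26, with power 80.7%. The stated 26 is reproduced and is not in question.

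**Inputs for the illustration.** n = 26 per group is from the protocol. The rest are assumptions, because the documents give no SD, effect or correlation for the scores:
- D, the true day 2 effect: 0.8 SD. This is the plan's figure for length of stay, borrowed here.
- ρ, the correlation between first and second scores: 0.3, 0.5 or 0.7.
- f, the average share of D already present at the first form.
- Scores are scaled to SD 1 and treated as normal.

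**Change, day 2 minus day 1.** The expected arm difference is D − fD = (1 − f)D. The SD of change is √(2(1 − ρ)) = 1.183/1.000/0.775 for ρ = 0.3/0.5/0.7.
- f = 0: difference 0.80, standardised 0.676/0.800/1.033.
- f = 0.5: difference 0.40, standardised 0.338/0.400/0.516.
- f = 1: difference 0, so the rejection rate is 5%.

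The noncentrality is the standardised difference × √(26/2), with 50 degrees of freedom.

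**ANCOVA on the day 2 score.** The expected adjusted difference is D − ρfD = D(1 − ρf). At f = 0 this is 0.80. At f = 0.5 it is 0.8 × 0.85/0.75/0.65 = 0.68/0.60/0.52. The residual SD is √(1 − ρ²) = 0.954/0.866/0.714. The ANCOVA powers below are simulated, because the simple formula ignores the variance added by the difference between arms in the first score.

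**Day 2 score alone.** The expected difference is D whatever f is.

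| Power at ρ = 0.3/0.5/0.7 | Change | ANCOVA | Day 2 alone |
|---|---|---|---|
| First form before first visit (f = 0) | 67/81/95% | 83/90/97% | 81% |
| A quarter of clown-arm first forms late, full effect present in them | 42/54/74% | 77/80/89% | 81% |
| Half the effect present at the first form (f = 0.5) | 22/29/45% | about 66 to 71% | 81% |

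In the quarter-late case f averages 0.25. The change contrast is then 0.75 × 0.8 = 0.60, and D(1 − ρf) gives about 0.74/0.70/0.66 for ANCOVA. Simulation gives 0.74/0.71/0.67. Both fall short of the true 0.80.

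**The case against.** The strongest reply is that Supplementary 1 and 2 are the CRFs themselves, which is where a completion time would normally stand, and they were not supplied. The text shows silence on timing, not the absence of a pre-visit form. A reader might infer that the trial has no baseline; the documents do not support that.

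The dilution also needs three things together: some first forms after a visit, an effect already present by then, and change meaning day 2 minus day 1. None is stated. The planned two-group tests would equally fit a direct comparison of each day's scores, in which nothing is subtracted. So the further inference that the well-being results would be uninterpretable does not hold either.

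Unadjusted testing is valid in itself. With a clean first form, simulated type I error was 4.9–5.0% for both change and ANCOVA. The gain from adjustment is precision on outcomes for which the plan claims no power, and over the change test it is small at ρ = 0.7.

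A reader might also conclude that ANCOVA on a late first score always loses power to the day 2 comparison. It does not: with a quarter of forms late it is slightly behind at ρ = 0.3, about level at 0.5 and ahead at 0.7. The reason to avoid it there is bias.

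All of this stands and limits the point. What remains is that the reference point for change is undefined in the supplied text, the order of form and visit is not secured there, and a collected score goes unused as a covariate.

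**Conclusion.** The point holds in a limited form. It concerns the secondary well-being scores and the CRF vital signs only; length of stay and the 26 per group are untouched.

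The loss is conditional. Where the three conditions hold, the change contrast shrinks to (1 − f) of the day 2 effect; at f = 0.5, power of the change test falls by 45/52/50 percentage points across the three correlations. Independently of timing problems, a clean first score used as covariate adds about 16/9/2 points over the change test and 2/9/16 points over the day 2 score alone.

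These sizes rest on assumed D, ρ and f and on normal scores. The actual items are 1-to-10 ratings, possibly skewed, so the figures show direction and order of magnitude rather than a forecast. The change is worth making because it is cheap, not because the trial's main conclusion is at risk.

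**What to change.** Two wording changes:

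1. In Study assessments, state that the first doctor and parent CRF, with vital signs, is completed after consent and before the first clown visit, within the same window after admission in both arms, and that the completion time is recorded. One instruction for every child also avoids the timing of the doctor's form hinting at allocation, in keeping with care decisions being "based solely on clinical judgment by pediatricians who were blinded to the study and not involved in it".
2. In Statistical analysis, state that the day 2 score is compared between arms by ANCOVA with the first score as covariate, rank-based if the scores are skewed, in place of an unadjusted test of change.

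If the first form cannot be kept ahead of the first visit, make the unadjusted day 2 comparison the main analysis. With part of the effect already present (f between 0 and 1, ρ positive), the change and ANCOVA estimates are both biased toward zero, while the day 2 comparison is not affected by f. If Supplementary 1 and 2 already set a pre-visit time, only the definition of the contrast and the second change are needed.

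The cost is CRF instructions and analysis wording, with no extra forms, staff or tests. The downside is that the first clown visit must wait for the first form.
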